- Participated in MOVE!, DPP, or another intensive weight management program (>4 sessions) in the past year,
- Have a history of bariatric surgery,
- Are pregnant, breastfeeding or become pregnant during the intervention period,
- Have a provider who states they should not participate,
- Have self-reported inability to read at 5th grade level.
- Currently take weight-loss medications or diabetes medication that may impact weight change
- Receive chemotherapy or cancer treatment
- Had metastatic cancer in the last 6 months
- Does not want to lose weight

We are excluding individuals with any of the above listed conditions as this will likely impact their ability to fully participate in this study. Additionally, some of these listed health conditions may limit physical activity. As this intervention includes telephone weight management counseling and reviewing of printed weight management materials, we are excluding participants without a telephone or participants who cannot read material written at the 5th grade level or above.

We will use phone screen and EHR information to verify inclusion and exclusion criteria.

Vulnerable Subjects

No vulnerable populations will be included as part of this weight management intervention study.

III. Methods and Procedures

[figure not shown]
We will conduct a cluster-randomized controlled trial of the GEM intervention at two healthcare systems in New York City: The VA New York Harbor Healthcare System (Manhattan campus) and Montefiore Medical Group (4 sites affiliated with New York City Research and Improvement Networking (NYC RING) practice-based research network. Participants will be randomized at the team level (19 teams with approximately 28 providers and 512 patients to achieve a sample size of 384 patients at 12 month follow-up for the primary outcome assessment). The primary care teams will be randomized using a random number generator (block randomization with block size of four) to either the GEM Intervention or Enhanced Usual Care arms. Randomization will be stratified by healthcare system (MMG and VA).

Intervention Arm – GEM

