- Encourage participation (using MI) in MOVE, DPP, or community-based programs/gyms
- Teach how to self-monitor weight, diet, and PA behaviors via pedometer, food log, and/or weight management apps (e.g. MOVE! Coach mobile^{70,71} on iPhones, My Fitness Pal⁷² on Androids)

- Provide brief MI and Brief Action Planning⁷³ to address barriers and increase patient self-efficacy
- Facilitate meetings with extended team members (e.g. health educators, dietitians, primary care physicians) if needed
- Enter a report for primary care teams into EHR from the GEM tool
- Communicate potential barriers/concerns to the team at baseline visit and as needed throughout the intervention period (e.g., via EHR notes, secure messaging system, telephone, and/or team meetings)
- ❖ **Telephone Coaching:** To achieve sufficient intensity according to USPSTF guidelines,¹⁰ we will incorporate 12 telephone coaching calls by a health coach over 12 months. Scheduled calls will occur every 2 weeks (biweekly) for months 1–3, monthly for months 4–6, and every other month (bimonthly) for months 7–12. GEM Intervention arm patients will receive a reminder call or an electronic reminder via MyHealtheVet or VA's Annie texting service to self-monitor their weight, food intake, and PA for at least 3 days prior to the coaching call. Studies suggest that episodes of short, consistent self-monitoring (for 3 days) reduce weight and may improve adherence.⁷⁴ Health coaches will use self-reported self-monitoring data (from pedometers, food logs, and smart phone apps) to determine goal adherence and counsel patients to encourage small changes.⁴⁹ Health coaches will document sessions in REDCap, help patients create new goals when appropriate, and use MI techniques to address barriers to behavior change. Patients will be able to contact health coaches via telephone for additional support. Patients will be reminded to discuss their goals during their next primary care visit (if scheduled).
- ❖ **Provider Role:** Providers in the GEM arm will provide 3–5 minutes of counseling, use clinical reminders to document this counseling, provide brief MI to address barriers (depending on time and patient needs), and discuss GEM-generated weight management goals during future visits. The GEM tool creates a report to communicate data to the participant's primary care team and generates a clinical reminder which facilitates documentation of primary team goal setting conversations and counseling.

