 - Health Coaches: Health coaching patients and data collection

VI. Subject Identification, Recruitment, and Consent/Assent

Method of Subject Identification and Recruitment

- ❖ **Primary Care Teams** – Primary care teams at each site that meet the eligibility criteria below will be separately assigned a number using a random number generator, and the first seven teams selected at each site will enroll in the study for a total of 19 primary care teams (11 VA and 8 MMG). Individual providers will be allowed to opt out of the study. We do not anticipate that providers will drop out once enrolled, based on the VA PROVE study where all 18 eligible teams and 51/52 providers participated for the duration of the study.⁶⁵ While pods (at MMG) and PACTs (at VA) have variable numbers of providers and patients, we will recruit 2-3 providers from each team prior to randomization to ensure similar numbers of teams, providers, and patients in each arm. **Table 2** (below) provides an overview of the staffing/patient population for each site.

[figure not shown]
Table 2: Description of PC staffing and patient populations at each of the VA and MMG sites (Data from the VA PC Almanac as of May 2015 or from MMG site director budget reports)

Site	#Teams (Pods or PACTs)	# Providers	Total # Patient s in PC	% Obese	% Female	% Hispanic or Latino
VA Brooklyn	12	24	13,219	32.7	11%	21%
VA Manhattan	11	28	13,813	26.7	8%	
MMG Bronx East	3	17	24,917	47.0	62%	38%
MMG Grand Concourse	2	11	17,841	41.0	67%	40%
MMG University Avenue	2	9	3,679	42.0	58%	79%
MMG Castle Hill	1	7	6,079	45.6	59%	58%

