❖ **Patient Recruitment (Figure 2 below)** – Using the Patients Health Information Systems and Technology Architecture (VistA), the VA's Health Information Technology system, and the Montefiore EPIC and Clinical Looking Glass systems, we will identify patients with upcoming primary care appointments who meet the eligibility criteria. A Research Assistant (RA) will confirm eligibility by EHR and provider review. One to two weeks before their baseline visit, eligible participants will be sent a letter signed by both the Principal Investigator (PI) and giving them the opportunity to opt out (i.e., request to not be contacted). The RA will call patients to recruit, screen for eligibility, and schedule the baseline. This allows enough time for all intervention components to be completed, and is responsive to patient scheduling preferences expressed in a similar recruitment strategy used in the VA PROVE study⁶⁵ and our pilot studies.

Eligibility will be based on the inclusion and exclusion criteria established for the study. Participation in the study is completely voluntary and all prospective subjects may refuse to participate or withdraw from the study at any given time.

Figure 2: Recruitment and Eligibility Screening

Process of Consent

Consent will be obtained by a research assistant trained in consenting protocols. Once subjects have been identified as eligible, the study will be described in detail and informed consent will be obtained from subjects who wish to participate. An audio-video consent form will also be described in detail for subjects who agree to have their study session audio recorded.

Subject Capacity

In order for subjects to be eligible to participate in the study, subjects must have the capacity to give informed consent. Capacity will be assessed with the set of inclusion and exclusion criteria that has been established specifically for this study. In short, participants must be at least 18 years of age, have access to a telephone, be able to travel for in-person evaluations, and not currently have functional impairments that limit

physical activity.

Subject/Representative Comprehension

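### Patients appear to be screened and consented after their team is randomised, with an unexplained provider veto and no stated masking of recruiters, so the arms could enrol different kinds of patients

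*Combined protocol and SAP*

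**What the plan says.** **Allocation.** Methods and Procedures (section III) states that "Participants will be randomized at the team level", using "block randomization with block size of four" and stratifying by healthcare system. Section VI, under Primary Care Teams, adds that "we will recruit 2-3 providers from each team prior to randomization". No matching statement is made for patients.

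**Finding patients.** Section VI, Patient Recruitment: "we will identify patients with upcoming primary care appointments who meet the eligibility criteria". Then "A Research Assistant (RA) will confirm eligibility by EHR and provider review". A letter goes out one to two weeks before the baseline visit, and "The RA will call patients to recruit, screen for eligibility, and schedule the baseline". Process of Consent has a research assistant obtain consent, and Data Collection has a research assistant take the measurements.

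**Veto.** One exclusion criterion reads "Have a provider who states they should not participate". No grounds are required and no record of the reason is described.

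**Who knows the arm.** The GEM tool and the coach session take place at the baseline visit. Under Provider Role, GEM providers give counselling and "use clinical reminders to document this counseling"; they also receive the GEM report. Enhanced Usual Care gives providers no study task beyond follow-up as needed.

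**Analysis.** The 12-month comparison named first is an unadjusted Mann-Whitney test. The mixed model may adjust for baseline characteristics, given only as examples. Baseline balance is tested, but no action follows from the result.

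**The concern.** Randomising teams protects the comparison of teams. It does not protect the comparison of patients who are chosen after the team's arm is set. Two routes are open here. A provider who knows the arm may remove patients for reasons related to likely weight loss. An RA who knows the arm may present the study differently, so that different patients agree to join.

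Either route would make the arms differ at baseline on features such as readiness to change, which listed covariates are unlikely to capture. The difference in weight loss would then mix the effect of GEM with the effect of selection. Enrolling more patients does not shrink that bias.

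**Working it through.** **1. The plan's own figures.** 512 × 0.75 = 384 completers, as stated. 512 / 0.20 = 2,560 patients to screen, against the stated 2,615 (512 / 2,615 = 19.6%), which is close enough. The text gives no alpha, power, effect size, SD or ICC, so there is no power figure to reproduce.

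**2. Order of events.** Providers join before randomisation. Patients are found from upcoming appointments, which means rolling recruitment. GEM starts at the baseline visit, so the team's arm must be fixed by then. A GEM provider who has counselled one study patient and completed a reminder knows the arm when the next patient comes up for review. The date of randomisation relative to screening is not stated, so this is a strong inference and not a documented fact.

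**3. How large could a veto effect be?** All inputs in this step except the 384 completers and 19 teams are assumptions. Suppose there is no true effect, providers in one arm veto the share *q* of candidates they judge to have the worst prognosis, and the other arm vetoes none. Let *r* be the correlation between that judgement and 12-month weight change.

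- Shift in judged prognosis = φ(z_q) / (1 − q). For q = 10%: 0.1755 / 0.90 = 0.195.
- Spurious difference d = r × shift, in SD of the outcome.
- Completers per arm 384 / 2 = 192; per team 384 / 19 = 20.2. Design effect = 1 + (20.2 − 1) × ICC, which is 1.96 at ICC 0.05.
- Standard error = √(2/192 × design effect): 0.102 at ICC 0 and 0.143 at ICC 0.05.
- Chance of a false positive = 1 − Φ(1.96 − d/SE) + Φ(−1.96 − d/SE). This supposes that the test uses the correct standard error.

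| Vetoed in one arm | Shift | d for r = 0.2 to 0.5 | False positive, ICC 0 | False positive, ICC 0.05 |
|---|---|---|---|---|
| 5% | 0.109 | 0.02–0.05 | 5.5–8.3% | 5.3–6.7% |
| 10% | 0.195 | 0.04–0.10 | 6.7–15.9% | 5.9–10.5% |
| 20% | 0.350 | 0.07–0.17 | 10.5–40.3% | 7.8–23.2% |

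Vetoes made equally and for the same reasons in both arms would cancel. Only a difference between arms matters, and its direction is not known.

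**4. What the table leaves out.** It covers the veto only. Selection through the RA's approach to patients is not modelled, because the documents give nothing to size it with.

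**The case against.** The strongest reply is that much of the selection is out of providers' hands. Patients are identified from the electronic record against written criteria. Patients who do not want to lose weight are excluded in both arms, which narrows differences in motivation. One letter and one patient research consent form are described, with no versions by arm, and the baseline pre-survey comes before either arm's material. Balance is tested and the mixed model can adjust. This stands as partial protection. It does not cover an unrecorded veto, an unmasked recruiter, or unmeasured differences among patients who all want to lose weight.

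Four stronger readings are tempting, and the documents do not support them.

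- *Providers in both arms already know their arm when they review patients.* The text dates neither randomisation nor disclosure. The inference fits GEM providers from about their first patient; nothing says that usual-care providers are told.
- *Providers can steer motivated patients in.* They do not refer patients. They can only remove them.
- *A 20% participation rate shows wide scope for the veto.* That rate applies to eligible patients, and a vetoed patient is not eligible. It bears on the RA's approach and on patient refusal.
- *The bias can be put in kg, or as a share of the detectable effect.* No SD, ICC or effect size is given. A 0.1 SD shift from a 10% veto would already need r = 0.1 / 0.195 = 0.51.

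The absence of masking must also be read with care. Figure 2, Appendix A (recruitment protocols) and part of the text before section VI, apparently including staff roles, were not available and may contain safeguards.

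**Conclusion.** The concern holds as a plausible and uncontrolled route to selection bias, not as a demonstrated bias. Teams are randomised, patients appear to be enrolled afterwards, providers may veto without a stated reason, and the text available masks no recruiter. The planned balance tests and optional adjustment would not remove the problem.

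The size is unknown. Veto scenarios with assumed shares of 5% to 20% and correlations of 0.2 to 0.5 give about 0.02 to 0.17 SD. At the low end the false-positive rate barely moves from 5%; at the high end it reaches 23.2% at ICC 0.05. These are illustrations and not bounds, since the difference between arms could also be nil. The change is worth making because it costs little.

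**What to change.** 1. **Mask the recruiters throughout recruitment.** The RAs who recruit, screen, consent and take baseline measurements should not have access to team allocation at any time while patients are being enrolled. Releasing the arm after each patient's baseline entry is not enough, because one release reveals the arm for every later patient of that team. Use baseline slots of the same length in both arms (the GEM content takes 20 + 30 = 50 minutes, against handouts), and one letter and one phone script. The health coach, who already gives the arm-specific material, takes over once baseline data are entered.
2. **Record the veto.** Add a reason field to the screening log, completed by the provider for each veto. Report screened, vetoed, declined and enrolled counts by arm and team. This reporting remains useful if recruitment has ended.
3. **Review early where feasible.** For patients already identifiable, take the provider review before the team's arm is released. Do not require a full-panel review. Table 2 implies about 13,813 × 0.267 / 28 = 132 obese patients per provider at VA Manhattan, before other exclusions and before adding overweight patients with a comorbidity, and such lists would go stale under rolling recruitment.

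The cost is equal-length slots, an access restriction in REDCap and one extra field, with no added staff. Health coaches also collect data, so the handover point must be written down. The Debriefing section says nothing is purposely withheld from subjects, so the consent wording should make clear when patients learn their arm. Patients or providers may sometimes break the masking; this should be logged.
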